11.2 Serious Adverse Experiences (SAE)

An SAE is defined as any AE occurring at any dose that results in any of the following outcomes:

- death
- a life-threatening adverse experience
- inpatient hospitalization or prolongation of existing hospitalization
- a persistent or significant disability/incapacity
- a congenital anomaly/birth defect

Other important medical events may also be considered an SAE when, based on appropriate medical judgment, they jeopardize the subject or require intervention to prevent one of the outcomes listed.

11.2.1 Serious Adverse Experience Reporting

Study sites will document all SAEs that occur (whether or not related to study drug) per SFDA Guidelines. The collection period for all SAEs will begin after informed consent is obtained and end after procedures for the final study visit have been completed.

In accordance with the standard operating procedures and policies of the local Institutional Review Board (IRB)/Independent Ethics Committee (IEC), the site investigator will report SAEs to the IRB/IEC.

12 DISCONTINUATION AND REPLACEMENT OF SUBJECTS

12.1 Early Discontinuation of Study Drug

A subject may be discontinued from study treatment at any time if the subject, the investigator, or the Sponsor feels that it is not in the subject's best interest to continue. The following is a list of possible reasons for study treatment discontinuation:

- Subject withdrawal of consent (or assent)
- Subject is not compliant with study procedures
- Adverse event that in the opinion of the investigator would be in the best interest of the subject to discontinue study treatment
- Protocol violation requiring discontinuation of study treatment
- Lost to follow-up
- Sponsor request for early termination of study
- Positive pregnancy test (females)

If a subject is withdrawn from treatment due to an adverse event, the subject will be followed and treated by the medical research team until the abnormal parameter or symptom has resolved or stabilized.

All subjects who discontinue study treatment should come in for an early discontinuation visit as soon as possible and then should be encouraged to complete all remaining scheduled visits and procedures.

All subjects are free to withdraw from participation at any time, for any reason, specified or unspecified, and without prejudice.

Reasonable attempts will be made by the investigator to provide a reason for subject withdrawals. The reason for the subject's withdrawal from the study will be specified in the subject's source documents Refer to Section 10 for early termination procedures.

12.3 Withdrawal of Subjects from the Study

A subject may be withdrawn from the study at any time if the subject, the investigator, or the Sponsor feels that it is not in the subject's best interest to continue.

All subjects are free to withdraw from participation at any time, for any reason, specified or unspecified, and without prejudice.

Reasonable attempts will be made by the investigator to provide a reason for subject withdrawals. The reason for the subject's withdrawal from the study will be specified in the subject's source documents. As noted above, subjects who discontinue study treatment early (i.e., they withdraw prior to Visit 1) should have an early discontinuation visit. Refer to Section 10 for early termination procedures. Subjects who withdraw after Visit 1 should

be encouraged to come in for a final visit (and the procedures to be followed would include those for their next scheduled visit).

12.4 Replacement of Subjects

Subjects who withdraw from the study treatment will be replaced.

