4 STUDY DESIGN

4.1 Study Overview

This is a single center, open-label, controlled, randomized, phase II clinical trial. 200 of subjects are planned. Each subject will be administered a single dose (500 mg) of study drug twice daily for 10 days. Subjects will be assigned to the treatments in random order. Evaluations will be taken daily for evaluationg symptoms imrovpment.

Screening data will be reviewed to determine subject eligibility. Subjects who meet all inclusion criteria and none of the exclusion criteria will be entered into the study.

The following treatment regimens will be used:

- Experimental treatment NS at the following dose 500 mg twice daily
- Comparator Standard care for COVID-19

Total duration of subject participation will be 14 days. Total duration of the study is expected to be 12 months.

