8 STUDY TREATMENTS

8.1 Method of Assigning Subjects to Treatment Groups

Up to 200 eligible patients will be randomly assigned to treatment or control groups in a 1:1 ratio using a computer-generated randomization scheme developed by http://www.randomization.com.

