8.3 Formulation of Test and Control Products

SFDA-licensed Marnys CUMINMAR Nigella sativa oil 500mg softgel oral capsules.

No control product will be used.

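### Section 12.4 replaces subjects who stop study treatment after randomisation; it acts mainly on the NS arm and leaves allocation and analysis of those concerned undefined

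*Combined protocol and SAP*

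**What the plan says.** Section 12.4 reads in full: "Subjects who withdraw from the study treatment will be replaced". It has no cut-off at randomisation or first dose, no allocation procedure, and nothing on the data of the person replaced.

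The trigger is described in section 12.1, which is headed as discontinuation of study drug. It introduces its reasons with "The following is a list of possible reasons for study treatment discontinuation", so the two terms are used interchangeably. The reasons include adverse events, protocol violations and "Subject is not compliant with study procedures". The subject, the investigator or the sponsor may each initiate stopping on a judgement of the subject's interest, and section 13 leaves it to the sponsor whether a violation leads to withdrawal. Those who stop "should be encouraged to complete all remaining scheduled visits and procedures".

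On the arms, section 4.1 describes an open-label trial with two regimens, "Experimental treatment NS at the following dose 500 mg twice daily" and "Comparator Standard care for COVID-19". Section 8.3 adds "No control product will be used". On allocation, section 8.1 says "Up to 200 eligible patients will be randomly assigned to treatment or control groups in a 1:1 ratio", while section 14.5 treats 200 (100 per arm) as a minimum. Section 14.1 defines one analysis set, the subjects who were dosed. No intention-to-treat set appears anywhere.

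**The concern.** Replacing randomised patients makes the composition of an arm depend on something that happens after randomisation. Here the event is stopping the study drug, which on the natural reading has no counterpart among controls. The decision can be made by people who know the arm and can see the symptom course, and the primary endpoint (section 5.1) is itself a count of symptom-free days.

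The text does not settle what replacement means in practice. Site staff would have to decide during the trial who fills the place, by what mechanism, and whether the first patient still counts. If those choices lead to NS patients with poor recovery being exchanged for new ones while similar controls stay in, the NS recovery rate rises without any drug effect.

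**Working it through.** **Step 1: what each reading of 12.4 implies.** The plan gives no replacement or withdrawal figure to reproduce. The 100 per arm from section 14.5 is taken as given.

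- *Replacement takes the next slot on the 1:1 list.* Allocation stays random, but about half the replacements become controls. With 10 NS withdrawals, 10 replacements give about 5 NS and 5 control, so NS patients still on treatment number about 100 − 10 + 5 = 95. The arm is not reliably refilled.
- *Replacement is placed directly in NS.* That patient is not randomised, against section 8.1. Refilling to 100 NS completers takes 100/(1 − w) NS patients for a withdrawal fraction w: 105, 111 and 125 at w = 5%, 10% and 20%, against 100 controls.
- *Replaced patient is dropped.* This conflicts with section 14.1 if the patient was dosed. If the patient withdrew before a first dose, 14.1 itself leaves the patient out.
- *Replaced patient is kept.* Once enrolment is full the total passes 200, which section 8.1 does not allow and section 14.5 does.

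**Step 2: size of the bias if withdrawn NS patients are swapped out.** These inputs are assumptions, since the documents give none: true recovery p = 0.50 in both arms, a fraction w of the NS arm swapped out once, and a share s of those being non-recoverers. The NS rate after swapping is

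p − w(1 − s) + w·p.

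For w = 0.10 and s = 1: 0.50 − 0 + 0.05 = 0.55. For w = 0.10 and s = 0.75: 0.50 − 0.025 + 0.05 = 0.525.

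The chance of a false result favouring NS comes from exact binomial enumeration of a pooled two-proportion z test at two-sided 0.05, 100 per arm, control rate 0.50. I use this test as the ordinary one for two proportions; the plan names a t test.

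| w | s | NS rate | Chance of false result favouring NS |
|---|---|---|---|
| 0 | – | 50% | 2.8% |
| 10% | 1 | 55% | 11.4% |
| 20% | 1 | 60% | 30.9% |
| 10% | 0.75 | 52.5% | 6.0% |
| 20% | 0.75 | 55% | 11.4% |
| 10% or 20% | 0.5 | 50% | 2.8% |
| 10% | 0.25 | 47.5% | 1.2% |
| 20% | 0.25 | 45% | 0.4% |

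The reference value is 2.8%, the exact rate for this test in one direction; the nominal rate is 2.5%. If replacements can themselves stop and be replaced, the NS rate becomes (p − w(1 − s))/(1 − w). For w = 10% and 20% with s = 1 that is 0.50/0.90 = 55.6% and 0.50/0.80 = 62.5%, and the chances rise to 13.0% and 44.4%.

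**Step 3: if everyone is kept.** With NS refilled to 100 completers and all withdrawn patients analysed in NS, simulation (100,000 trials per scenario) gives essentially no bias and a two-sided type I error of about 5% at w = 5%, 10% and 20%, whether or not stopping tracks recovery. This supposes that directly placed patients resemble the randomised ones.

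**The case against.** The strongest reply is that 12.4 never says replaced patients are removed. Section 14.1 includes everyone dosed, and section 12.1 wants those who stop to keep attending. Read together, a dosed NS patient who stops remains in follow-up and in the analysis, and Step 3 then shows no bias. This stands. A reader might infer from 12.4 that bias towards NS is built in; the documents do not support that. Exclusion follows from the text only for NS patients who withdraw before a first dose, and it is 14.1 that causes it.

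The direction is also open. The reasons in 12.1 do not name lack of efficacy or clinical worsening, and in mild illness a patient who feels well may stop capsules early. The rows with s at or below 0.5 show no bias or the reverse.

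Three further inferences go too far:

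- That only NS patients can be replaced. Section 4.1 lists standard care as a regimen, and consent withdrawal and loss to follow-up can occur in controls.
- That the rule undoes the 1:1 randomisation. Replacements taking the next slot preserve it. Those placed directly in NS are not randomised, but the earlier allocation stands if all are analysed as assigned.
- That replacement simply breaches the cap in 8.1. Section 14.5 allows more than 200, so the problem is that the two sections disagree.

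What the reply leaves untouched is that a mandatory replacement rule works after randomisation, in an open-label trial, with its key steps unwritten.

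**Conclusion.** The point holds as a defect of specification that opens a route to bias. Section 12.4 requires replacement on a post-randomisation, partly discretionary trigger that falls mainly on the NS arm, and it settles neither how the replacement is allocated nor whether the replaced patient is analysed. Section 14.1 protects only partly, because NS patients never dosed are left out and no set of all randomised patients exists.

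The size is conditional. At 10% of the NS arm swapped out, the chance of a false result favouring NS runs from about 1% to about 11% as the share of non-recoverers goes from a quarter to all, against 2.8% without swapping. At 20% it runs from 0.4% to about 31%. The recovery rate, the withdrawal rates and the link between stopping and recovery are all assumed. That the trial is exploratory limits the consequences but does not make the rule workable.

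**What to change.** Change section 12.4 to: *Randomised subjects will not be replaced. A subject who stops study treatment stays in the assigned arm, is followed to Day 14 unless consent for follow-up is withdrawn, and is analysed in that arm.* Limit any replacement to screening failures before randomisation.

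Change section 14.1 to match: the primary analysis includes all randomised subjects in their assigned arm, including NS patients who took no dose and all controls. Without this, the new 12.4 would contradict 14.1 for undosed patients. Reconcile the maximum of 200 in section 8.1 with the minimum of 200 in section 14.5.

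The cost is a few sentences across these sections. Somewhat fewer NS patients will complete treatment and some outcomes may be missing, so precision falls slightly and the plan should say how a missing outcome is handled. Section 14.5 describes no drop-out allowance. If the sponsor wants 200 evaluable patients, enrolling more from the start does this without replacement: 200/(1 − d) gives 211, 223 or 250 for an assumed loss d of 5%, 10% or 20%.

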13 PROTOCOL VIOLATIONS

A protocol violation occurs when the subject, investigator, fails to adhere to significant protocol requirements affecting the inclusion, exclusion, subject safety and primary endpoint criteria. Protocol violations for this study include, but are not limited to, the following:

- Failure to meet inclusion/exclusion criteria
- Use of a prohibited concomitant medication

Failure to comply with Good Clinical Practice (GCP) guidelines will also result in a protocol violation. The Sponsor will determine if a protocol violation will result in withdrawal of a subject.

When a protocol violation occurs, it will be discussed with the investigator and a Protocol Violation Form detailing the violation will be generated. This form will be signed by a Sponsor representative and the Investigator. A copy of the form will be filed in the site's regulatory binder and in the Sponsor's files.

14 STATISTICAL METHODS AND CONSIDERATIONS

14.1 Data Sets Analyzed

All dosed subjects will be included in data analysis

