	o Compliments (c3, c4),
	o Chest X-ray, CT scan
	o COVID-19 PCR
	o Immune phenotype (CD3 T Cell, CD4 T Cell, CD8 T Cell, CD19 B Cell, CD20 B Cell, NK Cell).
OTHER EVALUATIONS	Inflammatory cytokines (IL-1β, IL-1Ra, IL-2, IL-6, IL-10, INF-alpha, INF-gamma, Eotaxin, RANTES & TNF-α).
SAFETY EVALUATIONS	Incidence of adverse events from the investigational drug or transfer to ICU
PLANNED INTERIM ANALYSES	When approximately 50% of patients have completed the study, an interim analysis for safety will be conducted by an independent data monitoring committee. Serious adverse events will be monitored by the research team on an ongoing basis throughout the study.
STATISTICS Primary Analysis Plan	After 10 days of intervention, the Proportion of patients who clinically recovered on day 14 will be compared with control group. Student t test will be used to compare means of both groups.
Rationale for Number of Subjects	To achieve a power of 80% and a two-tailed p-value of <0.05 of an assumed 40% difference between the proportion of patients with clinical cure among the NS group in comparison with the control group, a total of at least 200 patients assigned randomly into the two arms (ie 100 patients per arm) will be needed to be included in the study as calculated using G*Power version 3.1.9.2 (Heinrich-Heine-University Düsseldorf, Düsseldorf, Germany).

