8.7 Measures of Treatment Compliance

Subjects will be monitored on daily bases during the study period for their study drug intake and any adverse events.

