10 EVALUATIONS BY VISIT

10.1 Visit 1 (Day 1)

- 1. Review the study with the subject (subject's legal representative) and obtain written informed consent.
- 2. Assign the subject a unique screening number.
- 3. Record demographics data.
- 4. Record medical history, diagnosis date.
- 5. Record concomitant medications.
- 6. Randomize subject,
- 7. Dispense study drug,
- 8. Initiate subject diary in CRF.

10.2 14 days monitoring

- 1. Record patients' symptoms
- 2. Record any Adverse Experiences and dosing compliance.
- 3. Concomitant medications review.

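### The only analysis set is conditioned on dosing: it cannot hold the no-product control arm, and if controls are kept it can drop randomised patients from the NS arm alone

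*Combined protocol and SAP*

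**What the plan says.** Section 14.1 is a single sentence: "All dosed subjects will be included in data analysis". No as-randomised, intention-to-treat or per-protocol set appears anywhere else.

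The control arm has no product. Section 4.1 lists "Comparator Standard care for COVID-19", section 8.3 states "No control product will be used", and the synopsis enters NA for the control product. Under the synopsis primary analysis plan, "the Proportion of patients who clinically recovered on day 14 will be compared with control group".

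Section 8.1 says "Up to 200 eligible patients will be randomly assigned to treatment or control groups in a 1:1 ratio". At Visit 1 (section 10.1), randomisation is step 6 and "Dispense study drug" is step 7. Under section 8.7 subjects are "monitored on daily bases during the study period for their study drug intake".

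Section 12.4 provides that subjects who withdraw from study treatment are replaced, and says no more. Section 14.5 sets 200 randomised patients as a minimum. Section 12.1 asks patients who stop treatment to attend a discontinuation visit, after which they are to be "encouraged to complete all remaining scheduled visits and procedures".

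**The concern.** The rule that decides who enters the primary comparison cannot be applied as written, because one of the two arms has nothing to be dosed with. Someone will have to decide at analysis who counts, in a trial where allocation and outcomes are known.

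The obvious repair is to keep every control and only the NS patients who took a capsule. That compares a subset of one randomised arm with the whole of the other. The subset is defined by an event after randomisation, when the patient already knows the allocation. If patients who never start differ in prognosis from those who do, the comparison is biased, in either direction.

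Section 12.4 adds a second gap. Only NS patients have a study treatment to withdraw from, and the plan does not say whether a replacement is newly randomised or placed in the vacated arm, or whether the replaced patient's data stay in the analysis.

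**Working it through.** **Text, side by side.** The set requires dosing (14.1). Controls receive no product (4.1, 8.3, synopsis). The comparison needs controls (synopsis). These three statements cannot all hold. If controls are kept, the dosing condition can exclude NS patients only. Such patients can exist because randomisation precedes dispensing in 10.1. NS patients who took at least one dose and then stopped remain in the set, so the exclusion concerns never-dosed patients only.

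**Replacement count.** 8.1 caps randomisation at 200 and 14.5 requires no fewer than 200. Exactly 200 satisfies both, so any replacement beyond that breaks 8.1.

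**Size of the possible effect.** The plan has no figure to reproduce on this point. From the documents: 100 per arm, two-sided 0.05, Student t test. Assumed: no true effect, overall recovery rate b, share u of NS patients never dosed, and recovery rate r among them.

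- NS recovery after dropping them: (b − u·r)/(1 − u).
- Bias: u(b − r)/(1 − u).
- NS sample size: 100(1 − u), against 100 controls.
- Test: t = (p̂₁ − p̂₀)/√[s²(1/n₁ + 1/n₀)], with s² = [n₁p̂₁(1 − p̂₁) + n₀p̂₀(1 − p̂₀)]/(n₁ + n₀ − 2), referred to t on n₁ + n₀ − 2 degrees of freedom. Rejection probabilities are summed exactly over both binomial distributions.

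Example: b = 0.5, u = 0.10, r = 0 gives (0.5 − 0)/0.9 = 0.556 v 0.50, a bias of 5.6 points with 90 v 100 patients. Type I error is 12.0%, of which 11.7% favours NS. With r = 1 the picture reverses.

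| Overall recovery | Never dosed (NS) | n | Type I error, lowest to highest over r = 0–100% | If they recover at half the average rate |
|---|---|---|---|---|
| 50% | 0 (reference) | 100 v 100 | 5.6% | – |
| 50% | 2% | 98 v 100 | 5.5–5.7% | – |
| 50% | 5% | 95 v 100 | 4.8–6.3% | 5.1% |
| 50% | 10% | 90 v 100 | 5.1–12.0% | 6.8% |
| 70% | 0 (reference) | 100 v 100 | 4.9% | – |
| 70% | 5% | 95 v 100 | 4.8–8.7% | 5.8% |
| 70% | 10% | 90 v 100 | 4.9–23.2% | 9.2% |

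The reference values differ from 5.0% because the outcome is discrete. The same discreteness explains why some entries fall below their reference.

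**Withdrawers kept, new patients randomised.** If dosed withdrawers stay in, as 14.1 implies, and extra patients are newly randomised, type I error at 50% recovery is 5.0% (105 v 100), 4.9% (110 v 100) and 5.1% (120 v 100). Replacement handled this way causes no inflation.

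**The case against.** The best defence is that 14.1 says dosed subjects are included, not that undosed ones are excluded. The protocol uses dosing language loosely elsewhere: 4.1 describes every subject as receiving study drug, and 14.2 summarises baseline by dose level in a trial with one dose. On that reading the word simply means enrolled, and nobody is dropped. This is plausible, and it means the one-sided exclusion is one possible reading rather than a certainty. It does not rescue the sentence, which would still have to be corrected to say so.

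The second argument is that the harm is likely to be small. Randomisation and dispensing are consecutive steps of one visit, intake is checked daily, and nothing in the documents suggests that 5–10% would never start. The larger error rates need 10% undosed together with extreme recovery among them. This stands, and it limits the weight of the numbers.

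Third, the 200 limits in 8.1 and 14.5 might count different things, randomised in one and included in the other. Both sentences, however, speak of patients randomly assigned, so the conflict remains.

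Lastly, analysing everyone as randomised needs a rule for patients with no 14-day record. That is true, but it is a separate point: withdrawals and losses to follow-up raise it under the present wording too.

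**Conclusion.** The concern holds and should be fixed. It is certain that the only analysis set contradicts the control arm, and that 12.4 is silent on how replacements are allocated and on whether replaced patients' data are kept. The compared groups are therefore not defined as the randomised groups.

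The size and direction of bias are unknown. Under the assumptions above, the effect is negligible at 2% never dosed and small at 5% unless their recovery is extreme. It becomes material only near 10% with very different recovery, and it can favour or disfavour NS. The case for changing the text rests on the contradiction and on removing an avoidable one-arm exclusion, not on a forecast of inflated error.

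**What to change.** - **14.1:** replace with: *The primary analysis includes all randomised subjects in the arm assigned, regardless of treatment received, compliance or withdrawal from treatment.*
- **12.4:** delete it, which leaves 8.1 and 14.5 consistent at 200. Or replace it with: *Subjects who withdraw from study treatment remain in the analysis in the arm assigned; any additional subject is newly randomised under 8.1*, and change the cap in 8.1 to match.
- **10.2:** state that the 14-day symptom record continues for patients who never start or who stop treatment. Section 12.1 already points this way for those who stop.
- **Exposure set:** use intake of at least one NS capsule only for NS exposure and safety summaries.
- **14.2:** summarise baseline by randomised arm.

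**Cost.** The change is wording, plus some follow-up effort for patients who never start. The statistical price is dilution from never-dosed patients now counted under NS; dosed withdrawers are already kept, so they add none. Assume the never-dosed recover at the control rate, with true rates of 70% v 50% and 100 randomised per arm (power 83.2% with everyone dosed):

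- 5% undosed: NS rate 0.95 × 0.70 + 0.05 × 0.50 = 0.69; power 79.1% as randomised against 81.8% dosed-only.
- 10% undosed: NS rate 0.90 × 0.70 + 0.10 × 0.50 = 0.68; power 74.6% against 81.0%.

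For a 40-point difference (70% v 30%), which is one reading of the effect in 14.5, power is at least 99.9% either way at up to 10% undosed.
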